#### Schedule of Events

Tests	Screening Visit	Baseline Visit	3 Month Visit (at conclusion of CR, ± 2 weeks)	12 Month Visit (± 2 weeks)
Informed Consent	X			
Randomization		X		
CBC (without differential)		X	X	X
Serum Albumin		X	X	X
Blood Urea Nitrogen (BUN)		X	X	X
Creatinine (serum)		X	X	X
AST		X	X	X
ALT		X	X	X
Bilirubin (total)		X	X	X
Bilirubin (direct)		X	X	X
Fasting lipid panel		X	X	X
Blood sample collection for molecular & SASP markers		X	X	X
Frailty assessment	X	X	X	X
Mini-Mental State Examination (MMSE)	X		X	X

Katz Index of Independence in ADL		X	X	X
Stool sample (optional sub-study)		X	X	X
Food Frequency Questionnaire (optional sub-study)		X	X	X
Self-report of antibiotics, laxatives, and colonoscopy history		X	X	X

**H. Statistical analyses and power considerations:** This is a pilot study and will not be powered to detect specific effect sizes. Importantly, measures of variation from this study will be used to power future studies.

**I. Human study issues:**

**Human Subjects Safety:** An independent, internal data and safety monitoring board (DSMB) will oversee the progress and safety of the trial and will advise the investigators whether to continue, modify, or terminate the trial. Potential risks to participants may include side effects from metformin.

Protection of patient's identity will follow the Department guidelines for handling and storage of research data. Standardized systems to ensure patient confidentiality will be maintained.

Medication safety will be ensured by not giving metformin to anyone who has history of hypersensitivity to metformin or who have moderate-to-severe renal impairment (GFR<45mL/min/1.73m^2). Participants on metformin will discontinue the drug to prevent lactic acidosis if they will have a radiologic study with contrast, surgery, excessive alcohol intake, or any other precipitating factors. The only other serious adverse effect of hepatitis will be periodically monitored by blood tests, including serum bilirubin, ALT and AST.

**Early withdrawal of Subjects:** Participants with serious adverse effects from the medications will discontinue medication use, but will continue with the study visits, unless they wish to completely withdraw from the study. We will make arrangements for the participant to be seen by their primary MD for follow-up. At any other time, patients will contact the main study coordinator, if they develop and want to report any side effects. We will also discontinue medication use if the participants fail to follow the protocol or are unwilling to continue the prescribed medication.

Patients who discontinue the drug will come for their final check-up and will include frailty assessment, and blood draw for biomarkers. We would use intention-to-treat analyses and would not add any other subjects. The subjects who discontinue the study drug will be followed-up by a phone call at one month. If the discontinuation is due to serious adverse effect, the patient will be asked to contact the primary care provider and further management will be instituted.

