**Administration of Metformin** The gastrointestinal intolerance (diarrhea, nausea, bloating etc.) is associated with higher dose initiation and rapid dose escalation. The pharmacist under the guidance of an endocrinologist will start metformin at a lower dose (500 mg twice a day with meals) and increase the dose at one-week interval to a maximum tolerable daily dose up to 1.0 gm twice a day, depending upon patient's tolerance. Since metformin does not stimulate insulin secretion, hypoglycemia is rarely observed. Randomization to drug or placebo will be done by the statistician to ensure blinding. Administration and monitoring of metformin/placebo will be done by the study coordinator under the supervision of an endocrinologist, who will not be involved in the routine care or follow-up of these patients. The drug will be stopped during hospitalization for repeat angiography, or any acute condition that can adversely affect renal function or can cause lactic acidosis (infection, dehydration etc.). The study medication (placebo or metformin) will be restarted following hospital discharge according to the current FDA recommendations. Renal function will be monitored as a part of their clinical care on follow-up. The drug will be discontinued in patients reporting significant adverse effects.

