### **Plan for alerting the staff for side effects**

The most common side effects are gastrointestinal. To reduce the incidence of these side effects, the dose of metformin will be slowly increased and will be given with meals. In the event of intolerable gastrointestinal side effects, the participant will contact the study coordinator via phone call (provided at the time of consent and enrollment). The study coordinator will inform the Principal Investigator and will determine whether a dose reduction is needed (which will be done over the phone) or the participant needs an additional visit. The study coordinator will make a follow-up phone call in one week to inquire whether the side effects have improved/resolved. If they have, the participant will continue with the protocol. If the participant needs to come in due to severity of side effects or the side effects don't resolve, the PI will see the participant and in consultation with the endocrinologist will determine whether to continue the drug, lower the dose, or stop the drug. If the drug is stopped, the final measurements will be done at that time.

**Blinding:** To ensure blinding, we will take the following steps. The investigators will be blinded to the treatment assignment. The pill count, change in the metformin dose, adverse effect reporting, data entry in the case report form (CRF) will be done by the main study coordinator. Measurement of frailty, MMSE, Katz ADL is done by a second study coordinator who will be unaware of the drug assignment. The pharmacist will not be involved in the routine care or follow-up of these patients. If the discontinuation of study drug is due to serious adverse effects, the principal investigator will contact the primary care provider and further management will be instituted.

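### The stop rule for contrast studies and surgery names only metformin recipients and gives no restart, so it needs reconciling with the blinding, restart and final check-up text

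*Protocol*

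**What the plan says.** Five places in the protocol bear on this point.

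- **Section I, Human Subjects Safety:** "Participants on metformin will discontinue the drug to prevent lactic acidosis if they will have a radiologic study with contrast, surgery". The sentence goes on to excessive alcohol and other precipitating factors. It mentions neither placebo nor a restart.
- **Section G, Administration of Metformin:** "The drug will be stopped during hospitalization for repeat angiography, or any acute condition that can adversely affect renal function". The drug is also stopped for acute conditions that could cause lactic acidosis. Then: "The study medication (placebo or metformin) will be restarted following hospital discharge according to the current FDA recommendations". Allocation is described in the same paragraph: "Randomization to drug or placebo will be done by the statistician to ensure blinding".
- **Blinding paragraph:** "The investigators will be blinded to the treatment assignment", and "Measurement of frailty, MMSE, Katz ADL is done by a second study coordinator who will be unaware of the drug assignment". The main coordinator handles pill counts and dose changes, and whether that person is blinded is not stated.
- **Final assessments:** under Early withdrawal of Subjects in section I, "Patients who discontinue the drug will come for their final check-up and will include frailty assessment, and blood draw for biomarkers", with a phone call at one month. The same heading says that participants who stop because of serious adverse effects keep attending study visits. In the plan for alerting staff to side effects, "If the drug is stopped, the final measurements will be done at that time".
- **Appendix 1:** the label extracts describe a temporary interruption for contrast studies and for surgery, with later resumption.

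**The concern.** A stop rule in a blinded trial has to be one that blinded staff can follow without learning the allocation. The section I sentence depends on knowing who takes metformin. If it is applied as written, a participant whose drug is stopped before a contrast study is on metformin, and one whose drug continues is on placebo.

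The second issue is what kind of stop is meant. The sentence uses the verb discontinue, and so does the early-withdrawal text that leads to a final check-up. If a short procedural hold were handled as a discontinuation, that participant's last frailty score and biomarker sample could be taken close to an acute event and not at 12 months ± 2 weeks. Section H says that the trial's measures of variation will be used to power future studies, and section I says that no subjects will be added. With 12 participants, one mistimed final assessment is a visible part of that output.

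The triggering events are foreseeable. Recruitment screens inpatients having coronary interventions, patients with acute coronary syndrome are eligible, and the protocol itself anticipates repeat angiography.

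**Working it through.** The protocol states no figure on this point to reproduce. The check is mainly a comparison of texts.

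**Step 1: set the rules side by side.**

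| Source | Who is covered | Type of stop | Restart |
|---|---|---|---|
| Section I, Human Subjects Safety | Metformin recipients only | Discontinue, not qualified | None given |
| Section G, Administration of Metformin | Both arms named at restart | Stop around hospital admission | After discharge |
| Appendix 1 | Patients on metformin (drug label) | Temporary, for contrast and surgery | Described |

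The two body-text rules overlap for an inpatient angiogram and differ in scope and in type of stop. The section G restart depends on hospital discharge. An outpatient contrast scan or day surgery has no discharge, so in the body text only the section I sentence governs it, and that sentence gives no restart.

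**Step 2: test the rule against the blind.** The investigators and the frailty assessor are blinded, so they cannot tell to whom the section I sentence applies. Someone who knows the allocation could apply it. The action would then disclose the arm to anyone aware of both the event and the drug status. The frailty assessor would learn the arm only if that information reached them.

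**Step 3: trace the final check-up.** The early-withdrawal sentence covers patients who discontinue and makes no exception for a temporary hold. The neighbouring text gives a different path (visits continue) for serious adverse effects. Nothing says which path a procedural stop follows.

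**Step 4: size of one case.** Inputs: 12 participants, randomized 1:1 (Abstract), so 12/2 = 6 per arm.

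- Share of the whole sample: 1/12 = 8.3%.
- Share of one arm: 1/6 = 16.7%.

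**Step 5: frequency, for scale only.** The protocol gives no rate of contrast studies or surgery. Assume that a proportion p of participants has at least one such event in the year, with p from 0.10 to 0.30.

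- *Disclosure of allocation.* Both stopping and not stopping are informative, so all 12 participants count. Expected number = 12p = 1.2 to 3.6. Chance of at least one = 1 − (1 − p)^12 = 1 − 0.90^12 = 0.72, up to 1 − 0.70^12 = 0.99.
- *Early final visit.* Under a metformin-only rule, only 6 participants can be affected. Expected number = 6p = 0.6 to 1.8. Chance of at least one = 1 − 0.90^6 = 0.47, up to 1 − 0.70^6 = 0.88. This also requires that the literal reading in step 3 is followed.

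**The case against.** The strongest reply is that the protocol, read as a whole, already means a temporary hold of blinded study medication in both arms. Section G is the operational text. It stops the drug without limiting this to an arm, and it names placebo at restart. The section I sentence belongs to a risk narrative, where naming metformin recipients may only explain who is at risk of lactic acidosis. Nothing says that placebo participants carry on. Appendix 1 uses the same verb with the qualifier that the stop is temporary. On this reading the conflict is loose wording. Much of this stands: it probably reflects the intent, and inpatient angiography is covered. It does not supply a restart for outpatient events, and it leaves two different scopes in the text.

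A reader might infer two stronger conclusions that the documents do not support.

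- *That the rule cannot be carried out under the blind.* The statistician makes the allocation and the main coordinator is not said to be blinded, so the rule could be carried out. The cost is disclosure to others. A team that follows section G would need no code break.
- *That any stop triggers the final visit.* The sentence in the side-effects plan closes the pathway for gastrointestinal intolerance. The check-up in section I sits under early withdrawal, next to serious adverse effects, non-adherence and unwillingness to continue, and its one-month call fits a permanent stop. The procedural rule is under a different heading. An early final visit is a possible literal reading, not a stated consequence.

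It is also fair to say that this is an unpowered pilot. That lowers the stakes but does not remove them, since its purpose is to supply measures of variation.

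**Conclusion.** The point holds as a defect of wording with practical consequences. The section I stop rule is limited to one arm and has no restart. It does not match section G or Appendix 1, and following it literally would disclose allocation whenever such an event occurs. Outpatient contrast studies and surgery are left without a restart in the body text. These conclusions rest on the text alone.

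The risk to the 12-month assessment is conditional: it arises only if a procedural hold is handled as a discontinuation under the early-withdrawal text. If that happened once, it would affect 8% of the sample or 17% of an arm. How often it might happen is unknown, and the range in the working rests on an assumed event rate.

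**What to change.** Reconcile section G (Administration of Metformin), the plan for alerting staff to side effects, section I (Human Subjects Safety and Early withdrawal) and Appendix 1, so that they give one answer to each of three questions:

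1. Does the rule for contrast, surgery and other precipitants refer to blinded study drug in both arms?
2. Is the stop temporary or permanent, including for events without a hospital admission?
3. Which kinds of stop trigger the final check-up, and which leave the 12-month visit where it is scheduled?

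The aim is to preserve the blind and the scheduled 12-month assessment. The clinical content of the rule is for the sponsor and its clinicians, and none is proposed here.

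The cost is a change of wording in a protocol amendment. If the reconciled rule covers both arms, placebo participants may also have their study drug interrupted around such events.

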**Stopping Rules: Following rules will be applied to stop the study.**

Death of any participant. Following death of any participant, we will stop the study and analyze the cause of death. We will inform IRB and DSMB as well. If the cause of death is unrelated to the drug, then after informing IRB with the permission of DSMB, the study will be restarted. If death is directly related to the drug, the study will be stopped.

In case of nonfatal serious side effects observed in one patient, the drug will be stopped in that patient and trial will be stopped as well.

## Appendices:

### Appendix 1

## Contraindications, warnings, precautions, adverse reactions and overdosage of metformin.

(Sources:

[https://www.accessdata.fda.gov/drugsatfda\\_docs/label/2008/020357s031,021202s016lbl.pdf](https://www.accessdata.fda.gov/drugsatfda_docs/label/2008/020357s031,021202s016lbl.pdf)

and

<http://www.fda.gov/downloads/drugs/drugsafety/ucm494140.pdf>

## CONTRAINdications

Metformin are contraindicated in patients with:

1. Metformin is contraindicated in patients with an eGFR below 30 mL/minute/1.73 m .
2. Starting metformin in patients with an eGFR between 30-45 mL/minute/1.73 m is not recommended.
3. Known hypersensitivity to metformin hydrochloride.

4. Acute or chronic metabolic acidosis, including diabetic ketoacidosis, with or without coma. Diabetic ketoacidosis should be treated with insulin.

Metformin should be temporarily discontinued in patients undergoing radiologic studies involving intravascular administration of iodinated contrast materials, because use of such products may result in acute alteration of renal function.

## WARNINGS

### Lactic Acidosis:

Lactic acidosis is a rare, but serious, metabolic complication that can occur due to metformin accumulation during treatment with Metformin; when it occurs, it is fatal in approximately 50% of cases. Lactic acidosis may also occur in association with a number of pathophysiologic conditions, including diabetes mellitus, and whenever there is significant tissue hypoperfusion and hypoxemia. Lactic acidosis is characterized by elevated blood lactate levels ( $>5$  mmol/L), decreased blood pH, electrolyte disturbances with an increased anion gap, and an increased lactate/pyruvate ratio. When metformin is implicated as the cause of lactic acidosis, metformin plasma levels  $>5$   $\mu$ g/mL are generally found.

The reported incidence of lactic acidosis in patients receiving metformin hydrochloride is very low (approximately 0.03 cases/1000 patient-years, with approximately 0.015 fatal cases/1000 patient-years). In more than 20,000 patient-years exposure to metformin in clinical trials, there were no reports of lactic acidosis. Reported cases have occurred primarily in diabetic patients with significant renal insufficiency, including both intrinsic renal disease and renal hypoperfusion, often in the setting of multiple concomitant medical/surgical problems and multiple concomitant medications. Patients with congestive heart failure requiring pharmacologic management, in particular those with unstable or acute congestive heart failure who are at risk of hypoperfusion and hypoxemia, are at increased risk of lactic acidosis. The risk of lactic acidosis increases with the degree of renal dysfunction and the patient's age. The risk of lactic acidosis may, therefore, be significantly decreased by regular monitoring of renal function in patients taking Metformin and by use of the minimum effective dose of Metformin. In particular, treatment of the elderly should be accompanied by careful monitoring of renal function. Metformin treatment should not be initiated in patients  $\geq 80$  years of age unless measurement of creatinine clearance demonstrates that renal function is not reduced, as these patients are more susceptible to developing lactic acidosis. In addition, Metformin should be promptly withheld in the presence of any condition associated with hypoxemia, dehydration, or sepsis. Because impaired hepatic function may significantly limit the ability to clear lactate, Metformin should generally be avoided in patients with clinical or laboratory evidence of hepatic disease. Patients should be cautioned against excessive alcohol intake, either acute or chronic, when taking Metformin, since alcohol potentiates the effects of metformin hydrochloride on lactate

metabolism. In addition, Metformin should be temporarily discontinued prior to any intravascular radiocontrast study and for any surgical procedure.

The onset of lactic acidosis often is subtle, and accompanied only by nonspecific symptoms such as malaise, myalgias, respiratory distress, increasing somnolence, and nonspecific abdominal distress. There may be associated hypothermia, hypotension, and resistant bradyarrhythmias with more marked acidosis. The patient and the patient's physician must be aware of the possible importance of such symptoms and the patient should be instructed to notify the physician immediately if they occur. Metformin should be withdrawn until the situation is clarified. Serum electrolytes, ketones, blood glucose, and if indicated, blood pH, lactate levels, and even blood metformin levels may be useful. Once a patient is stabilized on any dose level of Metformin, gastrointestinal symptoms, which are common during initiation of therapy, are unlikely to be drug related. Later occurrence of gastrointestinal symptoms could be due to lactic acidosis or other serious disease.

Levels of fasting venous plasma lactate above the upper limit of normal but less than 5 mmol/L in patients taking Metformin do not necessarily indicate impending lactic acidosis and may be explainable by other mechanisms, such as poorly controlled diabetes or obesity, vigorous physical activity, or technical problems in sample handling.

Lactic acidosis should be suspected in any diabetic patient with metabolic acidosis lacking evidence of ketoacidosis (ketonuria and ketonemia).

Lactic acidosis is a medical emergency that must be treated in a hospital setting. In a patient with lactic acidosis who is taking Metformin, the drug should be discontinued immediately and general supportive measures promptly instituted. Because metformin hydrochloride is dialyzable (with a clearance of up to 170 mL/min under good hemodynamic conditions), prompt hemodialysis is recommended to correct the acidosis and remove the accumulated metformin. Such management often results in prompt reversal of symptoms and recovery.

## **PRECAUTIONS**

### **General**

*Macrovascular Outcomes*—There have been no clinical studies establishing conclusive evidence of macrovascular risk reduction with Metformin or any other anti-diabetic drug.

*Monitoring of renal function*—Metformin is known to be substantially excreted by the kidney, and the risk of metformin accumulation and lactic acidosis increases with the degree of impairment of renal function. Thus, patients with serum creatinine levels above the upper limit of normal for their age should not receive Metformin. In patients with advanced age, Metformin should be carefully titrated to establish the minimum dose for adequate glycemic effect, because aging is associated with reduced renal function. In elderly patients, particularly those  $\geq 80$  years of age, renal function should be monitored regularly and, generally, Metformin should not be titrated to the maximum dose.

Before initiation of Metformin therapy and at least annually thereafter, renal function should be assessed and verified as normal. In patients in whom development of renal dysfunction is anticipated, renal function should be assessed more frequently and Metformin discontinued if evidence of renal impairment is present.

*Use of concomitant medications that may affect renal function or metformin disposition*—Concomitant medication(s) that may affect renal function or result in significant hemodynamic change or may interfere with the disposition of metformin, such as cationic drugs that are eliminated by renal tubular secretion, should be used with caution.

*Radiologic studies involving the use of intravascular iodinated contrast materials (for example, intravenous urogram, intravenous cholangiography, angiography, and computed tomography (CT) scans with intravascular contrast materials)*—Intravascular contrast studies with iodinated materials can lead to acute alteration of renal function and have been associated with lactic acidosis in patients receiving metformin. Therefore, in patients in whom any such study is planned, Metformin should be temporarily discontinued at the time of or prior to the procedure, and withheld for 48 hours subsequent to the procedure and reinstated only after renal function has been re-evaluated and found to be normal.

*Hypoxic states*—Cardiovascular collapse (shock) from whatever cause, acute congestive heart failure, acute myocardial infarction and other conditions characterized by hypoxemia have been associated with lactic acidosis and may also cause prerenal azotemia. When such events occur in patients on Metformin therapy, the drug should be promptly discontinued.

*Surgical procedures*—Metformin therapy should be temporarily suspended for any surgical procedure (except minor procedures not associated with restricted intake of food and fluids) and should not be restarted until the patient's oral intake has resumed and renal function has been evaluated as normal.

*Alcohol intake*—Alcohol is known to potentiate the effect of metformin on lactate metabolism. Patients, therefore, should be warned against excessive alcohol intake, acute or chronic, while receiving Metformin.

*Impaired hepatic function*—Since impaired hepatic function has been associated with some cases of lactic acidosis, Metformin should generally be avoided in patients with clinical or laboratory evidence of hepatic disease.

*Vitamin B12 levels*—In controlled clinical trials of metformin of 29 weeks duration, a decrease to subnormal levels of previously normal serum vitamin B12 levels, without clinical manifestations, was observed in approximately 7% of patients. Such decrease, possibly due to interference with B12 absorption from the B12-intrinsic factor complex, is, however, very rarely associated with anemia and appears to be rapidly reversible with discontinuation of metformin or vitamin B12 supplementation. Measurement of hematologic parameters on an annual basis is advised in patients on Metformin and any apparent abnormalities should be appropriately investigated and managed.

Certain individuals (those with inadequate vitamin B12 or calcium intake or absorption) appear to be predisposed to developing subnormal vitamin B12 levels. In these patients, routine serum vitamin B12 measurements at two- to three-year intervals may be useful.

*Change in clinical status of patients with previously controlled type 2 diabetes*—A patient with type 2 diabetes previously well controlled on Metformin who develops laboratory abnormalities or clinical illness (especially vague and poorly defined illness) should be evaluated promptly for evidence of ketoacidosis or lactic acidosis. Evaluation should include serum electrolytes and ketones, blood glucose and, if indicated, blood pH, lactate, pyruvate, and metformin levels. If acidosis of either form occurs, Metformin must be stopped immediately and other appropriate corrective measures initiated.

*Hypoglycemia*—Hypoglycemia does not occur in patients receiving Metformin alone under usual circumstances of use, but could occur when caloric intake is deficient, when strenuous exercise is not compensated by caloric supplementation, or during concomitant use with other glucose-lowering agents (such as sulfonylureas and insulin) or ethanol.

Elderly, debilitated, or malnourished patients, and those with adrenal or pituitary insufficiency or alcohol intoxication are particularly susceptible to hypoglycemic effects. Hypoglycemia may be difficult to recognize in the elderly, and in people who are taking beta-adrenergic blocking drugs.

*Loss of control of blood glucose*—When a patient stabilized on any diabetic regimen is exposed to stress such as fever, trauma, infection, or surgery, a temporary loss of glycemic control may occur. At such times, it may be necessary to withhold Metformin and temporarily administer insulin. Metformin may be reinstated after the acute episode is resolved.

The effectiveness of oral antidiabetic drugs in lowering blood glucose to a targeted level decreases in many patients over a period of time. This phenomenon, which may be due to progression of the underlying disease or to diminished responsiveness to the drug, is known as secondary failure, to distinguish it from primary failure in which the drug is ineffective during initial therapy. Should secondary failure occur with either Metformin or sulfonylurea monotherapy, combined therapy with Metformin and sulfonylurea may result in a response. Should secondary failure occur with combined GLUCOPHAGE/sulfonylurea therapy or metformin XR/sulfonylurea therapy, it may be necessary to consider therapeutic alternatives including initiation of insulin therapy.

